Power analysis and sample size justification. The main assessment of outcome is the change from baseline in percent dense tissue. The hypothesized mean change in area of dense tissue in the soy isoflavone group will be a decrease between 10 and 15 percentage points on average, while the placebo group will remain about the same (6; 10-15). Using a two group t-test with a 0.05 two-sided significance level, and estimates of the SDs that range from 20 to 10, we will have 80% power to detect changes in mean percent of dense tissue of -10% to -20%. If we experience a 20 to 30% dropout rate, the study can still detect changes of -10% if $SD \leq 20$, and -15% or larger for $SD \leq 25$. Our choice of 100 patients per arm is robust to any violations of our assumptions, for example unanticipated study variation or higher dropout rates than expected. Additionally, we can expect the study to have even greater power than we estimate since the proposed analyses (ANCOVA, mixed models) exhibit greater power characteristics than the t-tests upon which our power analysis is based. With an estimated attrition rate of 15% over the length of the study, 100 subjects per arm should provide 85 evaluable subjects at the completion of the study. We will recruit until 200 women complete at least 1.5 years of supplement.

Results expected. Increasing the duration of consumption of soy isoflavones is expected to decrease circulating (and nipple fluid) ovarian steroids, mammographic

density, and volume of breast with parenchymal tissue relative to adipose tissue. We expect the rates of these decreases to be greater in the isoflavone group than in the placebo group. Proliferation markers in nipple aspirates and the presence of hyperplastic epithelial cells in nipple aspirates may indicate the degree of stimulatory effects of isoflavones on breast tissues. This study will show whether breast MRI which measures 3-D features of the breasts may be more sensitive in detecting breast density changes than mammography, which is a 2-D assessment. Ability to use MRI (no radiation exposure) to measure breast density will allow us to assess in the future whether soy pill supplementation intervention on breast density and breast cancer prevention may be more effective if initiated during puberty than during adulthood, as data from animal studies have shown. The effect of isoflavones on bone is hard to predict and will be examined in this study.

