Soy isoflavone pills and maltodextrin placebo pills. The make-up of the isoflavones is the same as that which exists naturally in soy. We believe studying the effect of the two soy isoflavones at their naturally occurring ratio is a pre-requisite to contemplating a study that addresses the effect of different ratio or the individual isoflavone. The total amount of isoflavones in each tablet will be maintained constant through formulation. The formulation consists of, for example, 125 mg Novasoy (50 mg of total isoflavones as aglycones) or equivalent weight of placebo material, 60 mg sorbitol, 3 mg magnesium stearate, 412 mg dicalcium phosphate with a total of 600 mg per tablet. [Note: Volunteers in this study will take 2 pills (=120 mg isoflavones as aglycones) per day.] For placebo, 10-DE maltodextrin (90% weight) and RT-175 caramel color (10% by weight) will be substituted for Novasoy [Note: Volunteers will take 2 tablets per day.] The relative amount of genistein/genistin to daidzein/daidzin does vary between lots of soybeans and this variation is a natural phenomenon. This ratio for Novasoy has varied between 1.1 to 1.3 (mean \pm SD: 1.2 ± 0.1) from lot-to-lot. However, we will use only one lot of Novasoy for the entire study. Therefore, the relative amount of the two isoflavones will be constant. All subjects (both treatment and placebo) will be given required daily intake of multi-vitamin and minerals. Vitamin pill will be packaged with treatment assignment pill in container for daily dosage and consumption.

Breast density: Breast density of subjects will be determined by both mammography and bilateral breast MRI at the outpatient Radiology Clinic at UTMB. Both tests will be performed during the luteal phase, as confirmed by obtaining a blood sample on the days of the breast density tests for measuring progesterone.

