Post-intervention follow-up: The pills for both the placebo and isoflavone arms of the study contain multivitamins, including riboflavin and minerals. Riboflavin produces a bright yellow color in urine after intake. The study participants were blinded to treatment assignment per study protocol, but this would not prevent them from second guessing the study arm that they were assigned to. Our study participants probably would have noticed a change in their urine color whenever they ingested study pills, and this color change would indicate to the study team (we analyzed their urine) their degree of adherence to taking the study pills. Additionally, subjects might second guess the study arm that they were assigned to. The study subjects knew that they were taking multi-vitamins but were never told of a possible urine color change, and none of the subjects asked about this urine color change.

The purpose of this post-diet follow-up is to find out what these guesses were. We will email study participants who have received a dietary assignment. We would like each subject to choose one of these three answers in the email: (i) I believe that I took the placebo (sugar) pill, (ii) I believe that I took soy isoflavone pill, or (iii) I don't have an opinion about which of these I took. The frequency for each answer by treatment assignment and an interaction between treatment assignment and answer will be analyzed by ANOVA. We hypothesize that, due to the yellow coloring of their urine, a higher percentage of subjects would guess that they were in the active isoflavone treatment group, because most study participants prefer to be assigned to the active treatment group, if choice was allowed. This information will provide us with data about whether riboflavin can also be an effective masking agent for treatment group assignment in future clinical trials, not just as a tracer of compliance of taking study pills. Masking of treatment assignment would have an added benefit of balancing the participation behavior among study groups, in addition to randomization. We will send the questions initially by email and, if no response, by regular postal mail. We will request a dedicated email address from UTMB's Information Service for this specific purpose.

The survey questionnaire is not expected to change risk of participation.

Clinical Procedures:

The flow chart below outlines the study procedures and timeline in month (mo) for each subject:

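### The treatment-guess survey names an ANOVA that, on the six answer frequencies, has no error term; its directional hypothesis has no comparator, and the design cannot credit riboflavin with masking (minor, ancillary)

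*Combined protocol and SAP*

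**What the plan says.** The survey is described under Post-intervention follow-up. It goes to everyone assigned to a study arm ("We will email study participants who have received a dietary assignment"), and each woman picks one of three answers: placebo, isoflavone, or no opinion.

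- **Analysis:** "The frequency for each answer by treatment assignment and an interaction between treatment assignment and answer will be analyzed by ANOVA".
- **Hypothesis:** "a higher percentage of subjects would guess that they were in the active isoflavone treatment group". The sentence attributes this to urine colour and adds "because most study participants prefer to be assigned to the active treatment group, if choice was allowed".
- **Intended use:** the survey is to supply "data about whether riboflavin can also be an effective masking agent" in future trials.
- **Exposure:** "The pills for both the placebo and isoflavone arms of the study contain multivitamins, including riboflavin and minerals". The section on the soy isoflavone and placebo pills agrees: "All subjects (both treatment and placebo) will be given required daily intake of multi-vitamin and minerals".

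The Statistical Analysis section deals with breast density, using mixed models for continuous outcomes. It gives no other method for the survey. No sample size, significance level, expected response rate or handling of non-response is stated for it.

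**The concern.** The answer is a single nominal outcome per woman, so the data are a 2 (arm) by 3 (answer) table of counts. The plan uses answer as a factor in an ANOVA without saying what supplies the error. Three things are at stake:

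- whether the named analysis produces a test at all;
- whether any named term addresses the stated hypothesis;
- whether the result can support a statement about riboflavin.

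A reader of the eventual report could otherwise take a result from this survey as evidence that riboflavin hides assignment, and carry that into the design of later trials.

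**Working it through.** **Inputs.** The two arms, three answers and one answer per woman come from Post-intervention follow-up. The plan gives no survey figure to reproduce. All answer splits below are assumptions, written placebo/isoflavone/no opinion. Responder numbers are also assumptions: 100 per arm for the tables, and 85 per arm borrowed from the breast-density calculation ("100 subjects per arm should provide 85 evaluable subjects at the completion of the study").

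**Step 1: degrees of freedom.** Parameters = 1 (intercept) + 1 (arm) + 2 (answer) + 2 (interaction) = 6. Observations = 2 x 3 = 6 frequencies. Error df = 6 - 6 = 0, and fitting the model confirms this. Dropping the interaction frees 2 df, but those 2 df are the interaction itself.

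**Step 2: does the interaction test the hypothesis?** The chi-square is the 2-df arm-by-answer test. The last column pools the arms, with an exact two-sided binomial p-value against one half.

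| Assumed split, 100 per arm | Arm-by-answer chi-square | Isoflavone guesses among opinions |
|---|---|---|
| Both arms 20/60/20 | 0.00 (p = 1) | 120/160 (p = 1.8e-10) |
| Both arms 60/20/20 | 0.00 (p = 1) | 40/160 (p = 1.8e-10) |
| Both arms 20/20/60 | 0.00 (p = 1) | 40/80 (p = 1) |
| Placebo arm 60/20/20, isoflavone arm 20/60/20 | 40.0 (p = 2.1e-9) | 80/160 (p = 1) |

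The first row is the hypothesis as stated, the second its reverse, and the third a mainly undecided sample. The interaction is zero in all three. It responds only in the fourth row, where women guess their own arm. It therefore answers whether guesses depend on assignment, which is a different question from whether guesses lean towards isoflavone.

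**Step 3: riboflavin.** Riboflavin does not vary between arms, so no arm comparison can estimate its effect on guessing. The three answers record neither whether the colour was noticed nor why a woman guessed as she did. A lean towards isoflavone in both arms is what the colour explanation predicts. Preference for active treatment, which the plan also mentions, would predict it with or without riboflavin.

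**Step 4: what a directional contrast needs.** A pooled binomial test alone is not enough.

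- *Only the isoflavone arm guesses correctly.* Take the placebo arm at 35/35/30 and the isoflavone arm at 15/55/30, 85 per arm. Expected isoflavone guesses are 0.35 x 85 + 0.55 x 85 = 29.75 + 46.75 = 76.5. Expected placebo guesses are 29.75 + 12.75 = 42.5. The pooled share is 76.5/119 = 64%, and in simulation the pooled test declares an isoflavone excess in 87% of runs, although the placebo arm shows none. The 2x3 chi-square on these expected counts is 0.85 x [2 x 10²/25 + 2 x 10²/45] = 0.85 x 12.44 = 10.6 (2 df, p = exp(-5.29) = 0.005), so the arm comparison tends to expose the problem.
- *Most women have no opinion.* At 5/15/80 in both arms the pooled test declares an excess in 81% of runs, although 80% expressed no view.
- *Unequal response.* With 60/20/20 against 20/60/20 and 50 against 85 responders, it declares an excess in 22% of runs.

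Hence the contrast should be reported within each arm, with the no-opinion share and the response counts alongside, and pooled only under a stated condition.

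**The case against.** The strongest reply is that ANOVA is loose wording. The sentence does name the quantity analysed (answer frequencies by arm) and the effect of interest. If a log-linear model was meant, the interaction is a 2-df test of independence and needs no separate error term. A split-plot analysis of each woman's answers also works. With no arm difference and a nominal 5%, simulated rejection rates were 4.9-6.1% for the log-linear reading and 4.7-6.5% for the split-plot, over assumed splits and 50-100 responders per arm. This stands as far as it goes: a sound test is close at hand and asks the same question as the chi-square. But the plan names neither model, and either would leave the comparator and riboflavin points untouched.

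A reader might infer more than the documents support, in four ways.

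- *That the plan inflates the false-positive rate.* This needs a reading in which several rows per woman are treated as independent. The plan does not say that.
- *That an answer main effect could not support the hypothesis.* It has no sign of its own, but the frequencies would be seen. If support also required isoflavone to be the most frequent answer, simulation at 85 per arm with the same split in both arms gave support in 99.4%, 0.0% and 0.0% of runs at 20/50/30, 25/25/50 and 50/20/30. If isoflavone need only exceed placebo, 25/25/50 gave 47%. What is missing is the comparator and the reading rule.
- *That the test would be picked after seeing the data.* The documents do not say when the model would be fixed.
- *That the plan claims proof about riboflavin, or sets out two rival causes.* It promises data on the question, and colour and preference can be read as one chain of reasoning. The limit on what may be concluded holds either way.

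**Conclusion.** The point holds as a minor defect in an ancillary survey. On the frequencies it names, the ANOVA is saturated (0 error df) and gives no test, and no unit of analysis or error term is stated to rescue it. The directional hypothesis has no comparator, and the interaction does not test it. With riboflavin in both arms and no question on colour or reasons, the survey cannot attribute guesses or masking to riboflavin. It can show whether guesses depended on assignment among responders, which is a useful result.

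The degrees-of-freedom count and the riboflavin limit rest on the documents alone. The simulated percentages depend on assumed splits and responder numbers and serve only to shape the fix. The breast-density and safety analyses are not affected.

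**What to change.** Replace the ANOVA sentence with the following.

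1. A Pearson chi-square test, or a Fisher-Freeman-Halton test, of the 2x3 arm-by-answer table, as the test of whether guesses depend on assignment.
2. For the directional hypothesis, a prespecified exact binomial test of isoflavone against placebo guesses among women giving an opinion, reported within each arm with confidence intervals. Show the no-opinion share and response counts by arm. Pool the arms, and read the result as support, only when isoflavone guesses are in excess in both arms and test 1 gives no sign of an arm difference.
3. A conclusion limited to whether guesses differed by arm among responders, with a statement that the design cannot show that riboflavin masks assignment effectively.

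State the significance level for test 1. A non-significant result should not be reported as proof of equal guessing: for assumed shares of 50% and 70% guessing isoflavone, a two-sided 0.05 comparison of two proportions has power of about 0.76 at 85 per arm and 0.53 at 50.

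The cost is a few sentences of analysis text. The data are the same, with no added procedure or contact with participants.

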 13. After completing 12 months of pill supplement, subjects will complete another Harvard DAQ (recall food intake frequency for the past 12 months of pill intervention) and will be given a pregnancy test, followed by a mammography, a breast MRI, and a DEXA bone density test.

14. Subjects will continue consumption of the assigned pill, have the 1-day visit to GCRC for blood draw and other study procedures once every three months (e.g. repeat steps 6 to 14) for another 12 months.
15. Pregnancy test will be performed whenever cycle length increases by >30% of each subject's usual length. Pregnancy test will also be performed no longer than 48 hrs prior to taking mammography and DEXA tests to ensure that pregnant women are not exposed to radiation. Gynecological examination including Pap smear will be done at the end of the study.
16. Transvaginal probe ultrasonography and endometrial biopsies will be performed when medically indicated, for example, if amenorrhea develops. This will be performed by Dr. [name].

Risk and Benefit Assessment:

The soy isoflavone are currently available as pills over-the-counter and are found in soy foods sold to the public. We will use isoflavone tablets provided by the Archer Daniel Midland Co., which we have used in the past several years for several preliminary studies. These isoflavones are isolated by repeated alcohol extractions of soy protein isolates or soy protein concentrates (different processing). Alcohol is then removed by evaporation and the residues used for tablet formulation. In this way, the make-up of the isoflavones is the same as that which exists naturally in soy. These pills are sold as nutritional products over-the-counter to the public. The placebo pills contain maltodextrin, a carbohydrate, and should have no biological effect at the dose, 150 mg, to be given to the subjects.

Populations consuming soy have reduced risk of breast and endometrial cancers, reduced mammographic density, and reduced hip fracture rate. The FDA has approved a health claim regarding soy consumption and risk reduction for cardiovascular diseases. There are no other known risks from soy isoflavones from population-based studies, as soy products are commonly consumed in many countries. However, adverse effects have not been previously looked for carefully, so it is possible that there are unknown risks.

Isoflavones are weak estrogens and have beneficial such as acting as selective estrogen receptor modulators. However, in cell cultures or in animal models, the estrogenicity and biological effects of soy isoflavones are often concentration- or dose-dependent much like estrogens, are cell-type specific as well as species-dependent.

For example, anti-fertility effects have been observed in sheep but not in other species. Under low estrogen conditions, low dose of isoflavones stimulate the growth of hormone-dependent breast cancer cells in cultures, but high dose of isoflavones inhibit breast cancer cell proliferation. Isoflavones have also been shown to stimulate breast cancer cell growth in ovariectomized mice but the stimulatory effect was significantly less than that shown for the female estrogen, estradiol. In this xenograph mouse model, only one of the two isoflavones, genistein, is used and the free form (naturally occurring is conjugated form) is used which may not simulate human soy exposure experience. The breast cancer stimulatory effect of genistein shown in cell cultures and in xenograph mice

has not been found in humans yet.

Isoflavones cause thickening of the uterine lining in some animal studies (mostly in rats) after the ovaries were removed but this has not been found in sub-human primates. Moreover, our preliminary studies showed that 16 weeks of soy consumption at the dose that we plan to use for this study by postmenopausal women did not have estrogenic effect on the endometrium suggesting that it may not have adverse effect on the uterus. Other small human studies published to-date found no adverse estrogenic effect on the uterine lining from taking soy containing isoflavones or isoflavone pills. In fact, the only available epidemiological study indicated a lower rate of endometrial cancer with soy consumption.

Lowering of female hormones due to prolonged soy isoflavone ingestion may lower bone density, which could increase the risk of eventually developing osteoporosis (thin bones) and bone fractures. But this is not a known risk. Soy isoflavones have been shown to improve bone mineral density in animals. Asian populations consuming high levels of soy have lower rates of hip fracture compared to western countries. Because the current available information does not allow us to estimate the benefit and the risk of soy consumption on bone density, observations about bone is a part of this study. The risk of osteoporosis might also be increased if subject's calcium intake is not sufficient during the study. Subjects will be advised to adjust their calcium intake if needed to maintain an adequate intake.

Potential adverse effects such as lengthening of the menstrual cycle and nipple fluid cytology will be looked for closely during this study. If menstrual cycle lengths increase by more than 2 weeks in 12% of the participants (e.g. 12 subjects) for more than 3 cycles, the pill assignment codes for these women will be examined to assess if this is intervention-related. If this is associated with treatment, the ovarian hormones of these subjects will be immediately analyzed. The luteal progesterone levels in these women should be less than 1 ng/ml. If cycle length increase persists in these women for longer than 3 months, breast density in these women will be assessed first by breast MRI (because this involves no radiation exposure) and is likely to show changes. The pill supplement will be terminated in these women, but will be continued in the remaining study subjects. If cycle lengths increase in more than 30% of participants and this increase is study related, the pill intervention will be terminated and end of study mammography, bone density test by DEXA, and breast MRI will be performed.

If women develop amenorrhea, transvaginal probe ultrasonography and endometrial biopsies will be performed to ensure no adverse effects on the uterus. [name]. (a co-investigator) will prescribe and perform these tests. Study subject will be provided with a written pathological report for consultation with subject's own primary physician. Reports will also be provided to the Medical Monitor.

The total amount of blood drawn during each GCRC visit is 50 or 60 ml (3.3 or 4.0 tablespoons). Each subject will have a total of 12 GCRC visits for the collection of baseline and intervention data study. The total amount of blood drawn will be 46 tablespoons in 26 months. Blood chemistries, liver and thyroid function, lipid levels, and

serum ferritin levels of study subjects will be assessed once every 3 months during the study. If ferritin levels fall below 8 ng/ml, an iron supplement will be recommended. With blood drawing, there is a possibility of pain, bruising and infection. Blood draw will be performed by trained professionals.

Other than discomfort, there is no other known risk associated with nipple aspiration. If subjects cannot tolerate nipple aspiration procedure, this procedure may be omitted from these subjects. Nipple aspiration will be performed by trained professionals.

Mammography and DEXA are standard clinical tests. In these two tests, there is some radiation exposure. The amount of radiation exposure from mammography and bone density test will be equivalent to that of flying from Boston to Los Angeles. Radiation exposure may increase the risk of developing cancer. Mammography and bone density test will be performed by trained nuclear medical technologists.

Metal objects pose a serious risk for a MRI procedure because they can be affected by the high magnetic field. Surgical clips and other metal implants can be pulled out of place and devices such as pacemakers will not work in the magnetic field. Prior to MRI, all metal objects including jewelry are removed. MRI will be performed by trained nuclear medical technologists.

There is a possibility of cramping, bleeding, infection, and uterine perforation with endometrial biopsies. Most women have a few cramps in the pelvis after endometrial biopsy procedure that may last off and on for a couple of days. It is also common to have a small amount of bleeding from the vagina. The most serious potential risk from this test is "perforation" of the uterus. This occurs if the biopsy Pipelle is inserted too far, with too much force and it breaks through the wall of the uterus creating a hole. This is a problem because it can result in bleeding or infection, but this is not very common. One study found no infection and uterine perforation after 250 biopsies using Pipelle. Even without perforation, some patients can get an infection or have heavy bleeding that may require special treatment.

There is no known risk associated with vaginal probe ultrasonography. Vaginal probe ultrasonography, Pap smears, and endometrial biopsies are performed by a licensed gynecologist.

There is a possibility that samples provided during this study may be used in other research studies, or might have some commercial applicability that is not presently anticipated, and that this will not benefit the subjects. There is risk of loss of confidentiality. To avoid this, the information and samples provided to the investigators will be identified by a code number rather than by name. Preventive medical care including gynecological care will be provided to study subjects before and after the study and if needed.

There is a possibility of loss of confidentiality. To prevent loss of confidentiality, the information and samples provided to the investigators will be identified by a code number, rather than by the subject's name. For additional precaution protecting against

loss of confidentiality, see the section “Disposition of Data”. All key research personnel involved in this research have completed the required Human Subject Training available at www.utmb.edu/him/him_roi/confiden.htm.

There are no established benefits to the study.

Precaution, symptoms, and treatment of allergic reactions to soy: During initial screening, past history of allergic reactions to foods will be acquired. If subjects have prior histories of food allergies to soy containing food, they will be excluded. Symptoms associated with food allergies are diarrhea, fever and rashes. If subjects experience these allergy-like symptoms after pill intervention, they will be advised to stop the pill for several days until the symptoms disappear. If these symptoms recur upon resumption of pill, the subjects will be discontinued from the remaining study. Subjects develop allergic reactions during the study will be treated as clinically indicated by a physician investigators ([name] or [name]) in this project. Subjects are also encouraged to consult their own primary physicians.

Cost of Participation.

The cost of tests done as part of the research, such as screening mammography, breast MRI, bone density test, screening Pap Smears, and screening tests for blood chemistries, liver function, lipid profile and thyroid function will be provided to the subjects at no cost. The costs of medical care and diagnostic tests (transvaginal probe ultrasound and endometrial biopsies) required for the evaluation of prolonged or absent menses and other adverse events possibly resulting from the pill supplement will also be provided to the subjects free of charge. The cost of follow-up diagnostic tests after an initial abnormal screening mammogram, such as spot compression and breast ultrasound, will be the subject's responsibility. The cost of HPV test after an abnormal Pap test result during the screening period will also be given free. These follow-up diagnostic tests after an abnormal screening test generally can be paid for by the subject's health insurance. The study pill will be provided free to the subjects. We will provide vitamins, iron and calcium supplements to all subjects regardless of pill assignment.

Remuneration.

Subject will be reimbursed for study visits to the GCRC for parking and travel expenses, and for time and inconvenience resulting from participating in the study. Subject will be informed of the amount of reimbursement before the study starts. Subject will be reimbursed after the completion of the first 4 baseline blood draw visits (\$200 for all 4 visits or \$50 per visit), and thereafter after the completion of every blood draw visit (\$75 per visit per 3 months for the first year of pill supplement and \$125 per visit every 3 months for the second year of pill supplement). If subject withdraw or become ineligible to continue prior to the completion of the study, subject will be reimbursed only up to the last completed blood draw visit. Other than medical care that may be provided and any other payment specifically stated in this consent form, there is no other compensation available for participation. Subject may be removed from the study, if subject cannot comply with the study procedures described in this consent form (for example, if subject do not take the pills, miss scheduled GCRC visits, blood draws and radiologic tests, or do

not provide food records, urine collections, menstrual records etc), if subject become pregnant, or if subject develop serious unexpected medical conditions.

Reporting of Serious and Unexpected Adverse Events:

Adverse experiences that are both serious and unexpected will be immediately reported by telephone within 24 hr and in writing within 3 days to: 1) UTMB IRB, 2) UTMB GCRC, and 3) UTMB Research Subject Advocate.

A UTMB IRB Adverse Event Report form will be used to report individual serious adverse event. For recurring adverse event, an aggregate report form will be generated to provide summary statistics for the study that will include resolution and potential protocol modification or study termination. The adverse event reports will include the name of P.I. ([name].) and co-investigators ([name]., [name]., and [name].), name of the study (Mammographic Density and Soy Isoflavones), UTMB IRB number (03-260) and UTMB GCRC protocol number (#635), the number of subjects enrolled to date, the number and type of serious and unexpected adverse events previously reported. The report of the medical monitor ([name]) and a follow-up report describing the resolution of the adverse event will also be provided.

The expected adverse events are lengthening of menstrual cycle by more than 2 weeks per cycle in the absence of pregnancy for more than 3 cycles, amenorrhea, unexpected vaginal bleeding, breast lumps, abnormal endometrial histology/cytology, abnormal nipple aspirate cytology, and abnormal blood chemistries. Unanticipated adverse events are breast cancer, ovarian cancer, uterine cancer, intercurrent illness and intercurrent injuries. Serious adverse events are life threatening drug interaction, death, breach of confidentiality, and hospital admission.

Disposition of Data: All notebooks, Harvard DAQ, data collection forms, signed copies of the informed consent, and PHQF relating to this study will be kept in the locked filing cabinets on the [name], Division of Human Nutrition, Department of Preventive Medicine and Community Health, [name] where PI's office is located. The electronic data will be stored on the UTMB PMCH server (pmch on utmbf4) and the Bioinformatics Core facility of GCRC until published, and then archived in CD ROMs at the end of the study. The records will be kept for at least five years after the completion of publications resulting from this support.

During active data collection (e.g. screening, baseline and pill intervention periods), the data collection forms have subjects' names (to avoid making mistake), but these names will be wiped out from the forms and questionnaire and replaced with the assigned IDs as soon as the subjects complete the study. The PHQF is part of the subject's medical records and will be filed as such as soon as the subjects complete the study.

Each subject will be assigned a screening ID, BA001 to BA999 according to the

order they sign the informed consent which is also the order they enroll in the study. There may be dropouts during screening/baseline period but the ID of the dropouts once assigned will not be replaced. The subjects who complete the baseline study and if qualify to continue the pill intervention part of the study will be re-assigned another ID as PL001 to PL999 according to the order they begin the pill intervention portion of the study. Randomization will be made using PL IDs. The IDs are assigned by the Pharmacist and the key to the IDs is kept in the lock filing cabinets during active data collection. The Study Coordinators, PI, Dr. [name] (co-investigator physician responsible for subjects' well-being), and the Medical Monitor have access to this key during this period. After the completion of study, the key will be kept at the locked filing cabinet at the PI's office and at this stage, the PI, [name] and the Medical Monitor have access to the key.

Sample, image and record labeling: an example using subject PL001:

- Blood: PL001-S01 to PL001-S99 for sera, stored at -80°C
- Blood cells: PL001-C01 to PL001-C99, stored in liquid nitrogen tank
- Urine: PL001-U01 to PL001-U99, collected in a jug containing sodium azide and glycerol, stored at -20°C
- Nipple aspirate: PL001-N01(L,R) to PL001-N99(L,R); L, left breast; R, right breast, stored at -80°C
- Mammography: PL001-MM1La,b,c,d, or e (left breast, a to e views), PL001-MM1Ra,b,c,d, or e (right breast, a to e views)
- MRI: PL001-MR1L (left breast), PL001-MR1R (right breast)
- Bone density: PL001-D01-L2, L3, or L4 (lumbar spine 2, 3 or 4), PL001-D01-H (hip)
- Food Records: PL001-FR01 to PL001-FR99

